Appendix 4. Participant Diary

Day of the month	1	2	3	4	5	6	7	8	9	10
Time Skin Swab Collected										
Time VIBLOK Swab Collected										
Time in case of genital area shaved										
Time in case of genital area waxed										
Time in case of other hair removal										
Specify other hair removal method if applicable										
Anti-HSV medication taken										
Symptoms										
No Symptoms										
Itching, burning, tingling										
Lesions (sores, blisters, ulcers, crusts)										
Other (describe below)										
Lesion Locations										
Genital (Men: penis, scrotum; Women: vagina, labia, vulva, groin, pubis)										
Rectal (perineum, perianal)										
Buttock										
Other: _____										

Day of the month		11	12	13	14	15	16	17	18	19	20
Time Skin Swab Collected											
Time VIBLOK Swab Collected											
Time in case of genital area shaved											
Time in case of genital area waxed											
Time in case of other hair removal											
Specify other hair removal method if applicable											
Anti-HSV medication taken											
Symptoms											
No Symptoms											
Itching, burning, tingling											
Lesions (sores, blisters, ulcers, crusts)											
Other (describe below)											
Lesion Locations											
Genital (Men: penis, scrotum; Women: vagina, labia, vulva, groin, pubis)											
Rectal (perineum, perianal)											
Buttock											
Other: _____											

CLJI WORLDWIDE
 VIBLOK SAfety and perFormancE Trial Protocol
 Date 01/MAY/2017

Day of the month	21	22	23	24	25	26	27	28	29	30	31
Time Skin Swab Collected											
Time VIBLOK Swab Collected											
Time in case of genital area shaved											
Time in case of genital area waxed											
Time in case of other hair removal											
Specify other hair removal method if applicable											
Anti-HSV medication taken											
Symptoms											
No Symptoms											
Itching, burning, tingling											
Lesions (sores, blisters, ulcers, crusts)											
Other (describe below)											
Lesion Locations											
Genital (Men: penis, scrotum; Women: vagina, labia, vulva, groin, pubis)											
Rectal (perineum, perianal)											
Buttock											
Other: _____											

Appendix 5. Participant questionnaire

Participant questionnaire and debriefing: to be filled out by the participant during visit 4.		
Question	Circle one option	Free text
I found VIBLOK	
1. Very easy to use2. Somewhat easy to use3. Difficult to use	
The use was	
1. Simple and clear2. Somewhat confusing3. Very confusing	
The VIBLOK user documentation was	
1. Excellent2. Adequate3. Inadequate	
If VIBLOK was available for use, I would	
1. Use it2. Use it only in very special cases3. Never use it	
What I liked best about VIBLOK was		
What I liked least about VIBLOK was		
What suggestions do you have for improving VIBLOK?

## 1. Introduction

### 1.1 Study objectives

The objective of the study is to assess the safety and performance of the VIBLOK cream in HSV-2 infected adults. It is expected that data from this study will support an application for the CE Mark.

#### Primary Endpoint

- The primary safety endpoint will be number of Serious Adverse Device Effects during minimally 26 days of VIBLOK use.

#### Secondary Endpoints •

##### Device performance:

- Comparison of HSV-2 DNA detection rate on days with asymptomatic shedding prior and after applying VIBLOK

- Comparison of HSV-2 DNA copy number on days with asymptomatic shedding prior and after applying VIBLOK

- Safety endpoints:
  - Total number, type, and duration of AEs after 24 days of VIBLOK use.

#### Exploratory Parameters

- Sub-analyses to explore relation of device performance to
  - Gender
  - Time between VIBLOK application and sampling
  - Shaving and waxing habits
  - HSV symptoms
- Participant satisfaction using VIBLOK as assessed on the participant questionnaire (appendix 5 of the study protocol).

#### 1.2 Study design

This is a prospective, non-randomized, comparative multi-center safety and performance trial.

Up to 84 participants are planned to be enrolled at up to 6 participating investigational centers in Europe. The enrollment period is expected to be approximately 11 months and participant follow-up for participants with a confirmed HSV-2 infection will last for 26 to 31 days. Participants will be assessed at the following intervals: at screening, during the first application, and approximately 14 and 28 days after first application.

Forty six adults with recurrent genital herpes due to HSV-2 will be instructed to apply daily VIBLOK. Participants will obtain external genital skin swabs once daily, before and 5-60 minutes after applying the cream in the external genital area, and maintain a diary of genital signs and symptoms (Figure 3 and 4, Appendices 2, 3, and 4 of the study protocol).

#### Schedule of Events

| Activity   | Treatment Period |         |          |         |         |
|--|------------------|---------|----------|---------|---------|
|  | Screening        | Visit 1 | FUP call | Visit 2 | Visit 3 |
| Informed Consent   | X                |         |          |         |         |
| Review Inclusion/Exclusion Criteria                      | X                |         |          |         |         |
| Medical History (including HSV history)                  | X                |         |          |         |         |
| Interim History (including HSV history)                  |                  | X       |          | X       | X       |
| Targeted Physical Exam (including external genital exam) | X                | X*      |          | X*      | X*      |
| HSV serology   | X                |         |          |         |         |
| Urine pregnancy test                                     | X                |         |          |         |         |
| Provide Study Device and/or training                     |                  | X       | X        | X       |         |
| Review device use adherence                              |                  |         |          | X       | X       |

|                               |  |  |  |  |   |
|-------------------------------|--|--|--|--|---|
| AE assessment                 |  |  |  |  |   |
| User Questionnaire            |  |  |  |  | x |
| Daily Swab Collection & Diary |  |  |  |  |   |

\* for women possibly including internal genital exam if symptomatic

### 1.3 Statistical hypotheses

#### Primary endpoint

SADE incidence after minimally 26 days of VIBLOK treatment, will be assessed by calculating the upper limit of the two-sided exact 95% Clopper-Pearson confidence interval which needs to be below 10%.

#### Secondary endpoints with respect to device performance

Within-participant HSV-2 DNA detection rate on days with asymptomatic shedding. For each person, the number of swabs on which shedding occurs only pre-intervention will be assessed, and then the number of swabs on which shedding occurs only postintervention will be subtracted. The following hypothesis will be tested:

$H_0$ : The number of swabs on which shedding occurs only pre-intervention is the same when compared to the number of swabs on which shedding occurs only post-intervention

$H_1$ : The number of swabs on which shedding occurs only pre-intervention is not the same when compared to the number of swabs on which shedding occurs only post-intervention

HSV-2 copy number on HSV DNA positive samples detected by quantitative real-time PCR on days with asymptomatic shedding will be tested using the following hypothesis:

$H_0$ : The HSV-2 copy number on which shedding occurs only pre-intervention is the same when compared to the HSV-2 copy number on which shedding occurs only post-intervention

$H_1$ : The HSV-2 copy number on which shedding occurs only pre-intervention is not the same when compared to the HSV-2 copy number on which shedding occurs only post-intervention

#### Secondary endpoint with respect to safety:

The total number and type of AEs after minimally 26 days of VIBLOK use will be analyzed descriptively only. No hypothesis will be tested.

#### Exploratory endpoints

The sub-analyses

- To explore VIBLOK's blocking ability in relation to
  - Gender
  - Time between VIBLOK application and sampling
  - Shaving and waxing habits
- Participant satisfaction using VIBLOK as assessed on the participant questionnaire

will be analyzed descriptively only. No hypothesis will be tested.

#### 1.4 Sample size justification

The primary endpoint is the SADE incidence at 28 days of VIBLOK usage.

With a sample size of 36, an exact two-sided 95% confidence interval for a single proportion will show that the SADE incidence is below 10% at an expected incidence of 0.1%. Taking into account a drop-out rate of 15%, the estimated sample size needed is 42 study participants applying the VIBLOK cream.

The secondary endpoint is VIBLOK performance.

Statistical analysis will evaluate whether the disagreement rate in positivity between the pre and post-treatment swabs is indicative of a decrease in detection frequency. For each person, the number of swabs on which shedding occurs only pre-intervention will be assessed, and then the number of swabs on which shedding occurs only post-intervention will be subtracted.

If this number averages above zero, it indicates that the detection rate is decreased following intervention, and therefore a protective effect of the intervention with regard to shedding. Since this number is not distributed according to a known distribution, it will be compared to zero using a non-parametric test, the Wilcoxon signed-rank test. With an 8% anticipated asymptomatic shedding rate, 80% power and type I error of 5%, 40 participants taking samples for 28 days are needed to show a 50% reduction post-intervention, i.e. after applying VIBLOK.

Taking into account a drop-out rate of 15%, up to 46 adults applying VIBLOK cream are needed.

#### Total number of participants to be enrolled

Taking into account an overall screening failure rate of 45% for absence of a confirmed HSV-2 infection, up to 84 participants will be enrolled to get to the required minimum of 46 adults applying VIBLOK.

#### 1.5 Randomization and blinding

This study is a single-arm open-label study. A randomization procedure is not used and there are no procedures necessary of maintaining the blind.

### 2. General issues for statistical analyses

#### 2.1 Visit windows

An overview of the visit windows is given below:

| Visit Number | Label on Output | Target time point
(Day) | Interval (Day) |
|--------------|-----------------|----------------------------|----------------|
| 0            | Screening       | > -21                      | ≤ 0            |
| 1            | Day 1           | 1                          | 1              |
| N/A          | Day 3           | 3                          | 2-5            |
| 2            | Day 14          | 14                         | 12-16          |
| 3            | Day 28          | 28                         | 26-31          |

## 2.2 Protocol violations

### 2.2.1 Definition of protocol violations

Protocol deviations are defined in accordance with ICH E3 as important protocol deviations related to study inclusion or exclusion criteria, conduct of the trial, participant management or participant assessment.

All important protocol deviations will be assessed prior to closing the clinical database as to exclusion of one or more analysis sets.

All important protocol deviations will be classified into the following categories:

- Informed consent not signed and/or dated
- Wrong version of the informed consent used
- Inclusion / exclusion criteria
- Missed visits
- Visit not within window
- Protocol required data collection / testing
- Other deviation

An important protocol deviation will lead to exclusion of the participant or part of the participant's data from at least one analysis set. Minor protocol deviations, like only few days out of the time window, may not lead to exclusion of any data. Refer to section 2.2.2 as to the procedure whether or not to exclude any data from the statistical analysis.

Premature discontinuation from the study for reasons such as withdrawal of consent or occurrence of adverse events will not be considered to be a protocol deviation. Planned assessments after premature discontinuation will also not be considered to be a protocol deviation.

### 2.2.2 Determination of protocol violations

The clinical study team will evaluate the list of important protocol deviations as to exclusion of data from analysis sets. The evaluation might be on an ongoing basis during the conduct of the study or once prior to closing the clinical database. The outcome of the evaluation of the important protocol deviations will be

- documented in an Exclusion Memo to be signed off by at least the Biostatistician, Study manager and Sponsor

- stored in a data table (for example a SAS-dataset or Excel spreadsheet) which will be attached to the clinical database

After the sign off of the Exclusion Memo and the generation of the data table, the clinical database will be locked.

### 2.3 Missing values and outliers/ implausible measurements

Missing values will not be replaced in the statistical analysis.

An investigation may be done concerning the sensitivity of the results of analysis to the method of handling missing values, especially if the number of missing values is substantial.

Assessments directly measured by the participant will not be subject to a reconciliation process.

Therefore, implausible measurements as described in the table below might be removed from the statistical analysis. However, the implausible measurements will be presented in individual data listings. Final decision whether or not to remove implausible measurements from the statistical analysis will be documented in the Exclusion Memo.

| Parameter | Implausible measurements                |
|-----------|---|
| Swab data | Before/after assessment                 |
| Swab data | Obvious mistake in date on the swab log |
|           |   |

### 2.4 Pooling algorithm for study centers

All study centers will be pooled in the statistical analyses. However, by center summary statistics will be presented for the primary efficacy parameter.

### 2.5 Analysis sets

#### 2.5.1 All enrolled set

The All Enrolled Set will consist out of screened participants who provided informed consent. Study specific data will not be collected for participants who fail any of the eligibility criteria and do not apply the study product; these participants will be recorded on a Screening Log where the reason for screening failure will be documented.

#### 2.5.2 As Treated Population

The As Treated (AT) Population will consist of all participants that were enrolled in the trial and that applied VIBLOK at least once.

#### 2.5.3 Per Protocol Population

The Per Protocol (PP) Population will consist of all participants who fulfil the protocol in the terms of the eligibility and that applied VIBLOK for at least 26 days.

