9.3. Analysis Sets

The *As Treated (AT) Population* will consist of all participants that were enrolled in the trial and that applied VIBLOK at least once.

The *Per Protocol (PP) Population* will consist of all participants who fulfil the protocol in the terms of the eligibility and that applied VIBLOK for at least 26 days.

The primary and secondary endpoints will be reported based on the AT population.

Descriptive and summary statistical analysis will also be performed on all primary and secondary endpoints on the PP population.

Prior to final statistical analysis, designated staff will develop a memo that describes the exclusions from analysis populations.

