9.5. Endpoints

9.5.1. Primary Endpoint

The primary endpoint for this clinical study is SADE incidence after minimally 26 days of VIBLOK treatment in the AT population. This analysis will be repeated for the PP population.

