#### **2.6 Multiplicity**

The primary endpoint for this clinical study is SADE incidence during minimally 26 days of VIBLOK use in the As Treated Population. This analysis will be repeated for the Per Protocol Population. Since the primary endpoint is a safety endpoint and all other statistical analyses are secondary endpoints no correction for multiplicity will be performed to prevent alpha inflation.

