### 5.2 Adverse Events

#### 5.2.1 Primary endpoint

The primary endpoint of this study is a safety endpoint:

The number of Serious Adverse Device Effects during minimally 26 days of VIBLOK use. A two-sided exact 95% Clopper-Pearson confidence interval will be calculated. The study will be considered a success in case the upper limit of the 95% confidence interval is below 10%.

The analysis will be based on the As Treated Population and repeated for the Per Protocol Population.

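### The supportive Per Protocol repeat of the SADE analysis loses any participant whose SADE ends VIBLOK use before day 26, so it can understate the incidence; the As Treated verdict is unaffected

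*SAP*

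**What the plan says.** SAP 2.5.3 defines PP as "all participants who fulfil the protocol in the terms of the eligibility and that applied VIBLOK for at least 26 days". Protocol 9.3 has the same rule, and the sample listing in SAP Annex III shows a participant removed from PP for too few days of treatment. Neither document makes an exception for stopping because of an adverse event. AT (SAP 2.5.2, Protocol 9.3) needs only one application.

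For the primary endpoint, SAP 5.2.1 states "A two-sided exact 95% Clopper-Pearson confidence interval will be calculated" and then "The study will be considered a success in case the upper limit of the 95% confidence interval is below 10" (per cent). The next paragraph adds "The analysis will be based on the As Treated Population and repeated for the Per Protocol Population".

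Other sections fix the rank of the two sets. Protocol 9.5.1 defines the primary endpoint as "SADE incidence after minimally 26 days of VIBLOK treatment in the AT population", and SAP 2.6 as "SADE incidence during minimally 26 days of VIBLOK use in the As Treated Population". Of PP, Protocol 9.3 says "Descriptive and summary statistical analysis will also be performed on all primary and secondary endpoints on the PP population".

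**The concern.** PP membership depends on how long a participant used the cream after baseline, and the outcome itself can cut that time short. A SADE that ends use before day 26 disappears from the PP repeat. If every SADE did so, PP incidence would be zero by construction.

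At stake is how the supportive result is read. A PP repeat normally shows whether the primary result holds among participants who followed the plan. Here agreement between PP and AT would say little about safety, because PP can lose the events that the analysis is meant to count. If AT failed on a single SADE, PP could print zero events and a limit below 10% beside it. The data are meant to support a CE Mark application, so that contrast should not arise from the definition of the set.

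**Working it through.** **Inputs from the documents.** Exact two-sided 95% Clopper-Pearson interval and 10% limit (SAP 5.2.1); 36 evaluable participants, expected SADE incidence 0.1%, drop-out 15% and 46 users (SAP 1.4, Protocol 9.1); AT and PP definitions (SAP 2.5.2 and 2.5.3).

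**Assumptions.** The share q of SADEs that end use before day 26 is not given; I use 0, 25, 50, 75 and 100%. The 15% drop-out is taken as independent of SADEs and as always falling before day 26. All 46 users are eligible.

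**1. The plan's own figure.** The upper limit for x events in n is the 97.5% quantile of Beta(x+1, n−x). For x = 0 this is 1 − 0.025^(1/n). It gives 10.003% for 0/35 and 9.74% for 0/36, so 36 is reproduced as the smallest n that passes with no event.

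**2. One SADE among 46 users that ends use early.**
- AT: 1/46, limit 11.53%, above 10%. One event needs at least 54 users to pass (1/53: 10.07%; 1/54: 9.89%).
- PP, no other early leaver: 0/45, limit 7.87%.
- PP, 7 further early leavers (15% of 46 = 6.9): 46 − 1 − 7 = 38; 0/38, limit 9.25%.

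**3. Direction of the bias.** Let p be the true SADE risk, e the chance that a participant with a SADE stops early, and d the same chance without one. Expected PP incidence is approximately

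p(1−e) / [p(1−e) + (1−p)(1−d)],

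which is below p only if e > d. If no participant with a SADE stopped early (e = 0, d = 0.15, p = 2%), it would be 0.02 / (0.02 + 0.98 × 0.85) = 2.3%, slightly above 2%.

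**4. How often the limit falls below 10%.** I enumerated all outcomes exactly for 46 users, with 15% drop-out for everyone and a further share q of SADEs ending use, so that 1 − e = 0.85(1 − q). The row q = 0 is the baseline from ordinary drop-out alone.

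| q | True risk 10%: PP below 10% | True risk 0.1%: AT fails, PP below 10% |
|---|---|---|
| 0 | 1.5% | 0.6% |
| 25% | 3.8% | 1.4% |
| 50% | 9.3% | 2.2% |
| 75% | 21.5% | 3.1% |
| 100% | 46.9% | 3.9% |

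AT passes only with no SADE: 0.9^46 = 0.8% of trials at a true risk of 10%, and 0.999^46 = 95.5% at 0.1%.

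At 0.1%, PP is below 10% in 89% (q = 0) to 92% (q = 100%) of trials. That is less often than AT, because PP falls below 36 participants in about 7% to 8% of trials and then misses the limit even with no event.

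**The case against.** The strongest reply is that nothing is decided on PP, and this stands. A reader might infer from the success sentence in SAP 5.2.1, which names no analysis set, that a favourable PP result could carry the trial. The documents do not support that: the following paragraph bases the analysis on AT, Protocol 9.5.1 and SAP 2.6 place the endpoint in AT, and Protocol 9.3 makes PP descriptive.

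Nor would the event be hidden. Protocol 5.3.1 keeps early discontinuers in the analysis, SAP 2.5.4 expects every user in the safety analysis, SAP 5.3 requires listings and narratives, and Annex III would list the exclusion.

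A reader might also see a contradiction with SAP 2.2.1, under which stopping early for reasons such as "occurrence of adverse events will not be considered to be a protocol deviation". There is none. That section says what counts as a deviation, while the 26-day rule is a separate exposure criterion. A participant can commit no deviation and still not belong to PP.

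The size also needs restraint. Part of each figure comes from ordinary drop-out, as the q = 0 row shows. The 47% needs a true risk 100 times the planned one, every SADE ending use, and 15% drop-out; with 25% drop-out (assumption) it is about 8%. Finally, a result restricted to 26 days of use has descriptive value, since short-exposure users without a SADE dilute the AT denominator.

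What remains is that the PP repeat of a safety endpoint applies an inclusion rule that the endpoint itself can break.

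**Conclusion.** The point holds for the supportive analysis only. PP incidence is biased downwards if SADEs end use before day 26 more often than other causes do. That condition is plausible, but the documents neither state nor quantify it, so it would go too far to say that PP is always biased towards zero.

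In the clearest case, one such SADE among 46 users, the upper limit moves from 11.5% (AT) to 7.9% (PP). Under the planned 0.1% incidence and 15% drop-out, AT failing beside a PP limit below 10% occurs in 0.6% to 3.9% of trials, and PP is usually the less favourable analysis. The larger percentages apply only if the true risk is far above plan.

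The AT result and the success decision do not depend on the PP definition. Severity is minor; confidence in the mechanism and the arithmetic is high.

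**What to change.** Add to SAP 5.2.1: *For the SADE endpoint only, the Per Protocol repeat covers all eligible participants who used VIBLOK at least once, with or without a SADE; the 26-day requirement does not apply.* Record the exception against SAP 2.5.3 and Protocol 9.3, and leave PP unchanged for every other endpoint.

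The 26-day rule should be lifted for everyone, not just for participants with a SADE. Keeping short-exposure users only when they had an event would select on the outcome and push the estimate up: with one SADE kept and 7 other early leavers dropped, 1/39 gives a limit of 13.5%, against 11.5% for 1/46.

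A cross-reference in SAP 5.2.1 that the 10% rule is judged on AT only is optional, since it restates existing text.

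The cost is one sentence in SAP 5.2.1, a note at the two definitions (the protocol note under Protocol 11.6), and no extra table. The PP SADE result will then lie close to AT, differing only by ineligible users, and it can look worse: one SADE and two ineligible users without one (assumption) gives 1/44, limit 12.0%. The result at full exposure is no longer shown as PP. If it is wanted, it can be reported separately and labelled as conditional on 26 days of use.
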